2 PURPOSE OF THE ANALYSES

This statistical analysis plan (SAP) contains detailed information about statistical analysis to be performed to test the therapeutic actions of kappa-opioid receptor antagonism. We propose a proof-of-concept study to evaluate the effects of sublingual buprenorphine (BUP; Subutex) combined with extended-release injectable naltrexone (NTRX; Vivitrol) in the treatment of comorbid PTSD and AUD. No formal interim analyses will be conducted. As such, all analyses described will be performed at the end of the study excluding any efficacy and/or safety summaries provided for the DSMB, which are described in Section 7.4.

The deliverable will be data that advances the understanding of KOR antagonistic pharmacology in the treatment of comorbid AUD and PTSD with the aim to inform a decision about proceeding with full development of soon-to-be marketed KOR antagonists for the treatment of comorbid AUD and PTSD. Finding a novel pharmacologic treatment approach to improve the clinical outcomes for

Veterans and military Service-Members with comorbid PTSD and AUD is the focus of this project, which aligns exceptionally well with the goals of the PASA Consortium.

3 STUDY OBJECTIVES AND OUTCOMES

3.1 Study Objectives

The **specific aim** of this study is to evaluate the effects of sublingual buprenorphine (BUP; Subutex) combined with extended-release injectable naltrexone (NTRX; Vivitrol) in the treatment of comorbid PTSD and AUD.

The **objectives** of this aim are to compare safety and efficacy endpoints in the treatment group versus placebo after 8 weeks (with an additional follow up period extending to 12 weeks).

The study team hypothesizes that the efficacy of BUP/NTRX in the treatment of comorbid PTSD and moderate-to-severe AUD will be greatest in the treatment group followed by a very minimal effect for the placebo group.

SAP version 3.0 was updated to remove the evaluation of the Fear Potentiated Startle (FPS) assessment from this primary SAP. The FPS was changed from a secondary objective to an exploratory objective in SAP version 2.0 due to the pause in the FPS assessment as a result of the COVID pandemic. Exploratory analyses of the FPS assessment will be included and described in a secondary supplemental SAP, as needed.

3.1.1 Primary Safety Objectives

1. Determine if adverse event rates, severity, and relatedness differ between the BUP/NLTRX group compared to the placebo group over the 8-week study period.

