The investigators have designed the study to include two weeks (from Week 12 to Week 14) to monitor the patient for drug discontinuation or withdrawal symptoms. The investigators will treat emergent psychological symptoms with psychosocial support and physical symptoms with the appropriate treatments, such as metoclopramide for nausea, NSAIDs for pain, clonidine for opioid-like withdrawal symptoms, and loperamide for diarrhea. Three to five days after Week 12 discontinuation of medication, the research nurse will call participant to check on emergent adverse symptoms

A caution that is included in the informed consent stating that in a situation when analgesia may be required in a patient who has received full blocking doses of XR-NTX, consideration should be given to regional analgesia, conscious sedation with a benzodiazepine, use of non-opioid analgesics, or general anesthesia. If opioid analgesia is required, the amount of opioid needed may be greater than usual, and the resulting respiratory depression may be deeper and more prolonged. In this case, a rapidly acting opioid analgesic that minimizes the duration of respiratory depression is preferred. XR-NTX can also diminish the benefit from opioid-containing cough, cold, and antidiarrheal preparations, which is listed as a warning in the informed consent. These warning are standard when treating patients with XR-NTX.

Side effects of XR-NTX that led to more discontinuation of treatment compared to placebo include the following: pain, tenderness, induration or pruritus at the site of the injection (3%), nausea (2%), headache (1%), and suicide-related events (0.3%). Other known non-serious side effects that differ from placebo include nausea (29% vs 11%), vomiting (12% vs 6%), diarrhea (13% vs 10%), abdominal pain (11% vs 8%), injection site reactions (65% vs 50%), arthralgia/arthritis (9% vs 5%), muscle cramps (5% vs 1%), rash (6% vs 4%), headache (21% vs

18%) dizziness (13% vs 4%), somnolence/sedation (5% vs 1%), and appetite decrease (11% vs 3%). XR-NTX has the capacity to cause hepatocellular injury when given in excessive doses (the margin of separation between the apparently safe dose of naltrexone and the dose causing hepatic injury appears to be five-fold. XR-NTX does not appear to be a hepatotoxin at the recommended doses used in this study.

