6.1.9 DURATION OF THERAPY

The duration of therapy is 12 weeks.

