8.3 ADVERSE EVENT ASSESSMENT AND FOLLOW-UP

AEs are collected from time of first dose taken after randomization through Week 14 follow-up visit. Study investigators follow all SAEs clinically until resolved or clinically stable. The occurrence of an AE or SAE may come to the attention of study personnel during study visits and interviews of a study participant presenting for medical care, or upon review by a study monitor. At each study visit, the LSI or trained designee asks the participant about the occurrence of AE/SAEs since the last visit. All AEs are captured on the appropriate CRF.

Information to be collected includes event description, time of onset, clinician's assessment of severity, relationship to study product (assessed only by those with the training and authority to make a diagnosis), and time of resolution/stabilization of the event. All AEs occurring while on study must be documented appropriately regardless of relationship.

Any medical condition that is present at the time that the participant is screened is considered as a baseline condition and not reported as an AE. However, if the study participant's condition deteriorates at any time during the study, it is recorded as an AE.

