10.4.4 SAFETY ANALYSES

The safety analyses population includes all randomized participants. These analyses will include those participants who have reported an adverse event as well as those who do not report an adverse event. The incidence of treatment emergent adverse events, type of adverse events, and frequency of withdrawals due to an adverse event will be summarized by treatment group. Appropriate statistical comparisons will be made between treatment groups in terms of 1) rates of adverse events, 2) discontinuation due to adverse events, and 3) side effect scales. Rates will be compared using time to event hazard analysis. Frequencies will be analyzed using the chi square or Fisher Exact test. The scales will be examined using non-parametric analyses when appropriate. This study is not powered as an equivalence study so the non-significance of differences between groups does not truly imply equivalence.

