4 STUDY METHODS

4.1 Overall Study Design and Plan

This randomized, double-blind, placebo-controlled, multi-site study evaluates the efficacy of SL-BUP combined with XR-NTX in the treatment of comorbid AUD and PTSD. Recruitment is based on convenience sampling of treatment-seeking veterans and active duty service members. Following screening and baseline visits, eligible patients are randomization to receive one of two treatments in a double-blind fashion for 12 weeks:

- Treatment A (SL-BUP 2mg and XR-NTX 380mg) or**
- Treatment B (SL-PLC and XR-PLC).**

The treatment allocation ratio for the treatment vs. placebo (PLC) regimens is **1:1** and is stratified by site, presence of concomitant antidepressants, and gender using a random permuted block scheme with variable block size (see below Figure). The study population will consist of ~ 90 Veterans with combat-related PTSD and co-morbid AUD. Detailed eligibility criteria for participant inclusion in this study are included in Section 4.2, below.

Study Design: RCT of KOR Antagonist in the treatment of Comorbid AUD and PTSD

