9.5 Safety Analysis Methods

9.5.1 Adverse Events

Any AEs will be listed and summarized by system organ class and preferred event term. Summaries will include the number of individuals experiencing events over the duration of the study. These summaries will be created for all AEs and AEs by severity (mild or moderate vs. severe or greater). Summaries will be provided by treatment group. If models can be run, point and confidence interval estimates of the risk difference will be obtained by modeling the probability of experiencing at least one adverse event. The model is specified with the equation:

$$g(E(Y_{ij})) = \beta_0 + \beta_1 \text{Treatment}_{ij} + s_i + \varepsilon_{ij}$$

Where $g(E(\cdot))$ indicates the identity link function on the expected value of Y , Y_{ij} is the occurrence of an AE outcome (any AE, any SAE, and any related AE) in subject i , β_0 is the intercept, β_1 is the treatment group coefficients, s_i is a random subject effect, and ε_{ij} is the residual error term.

Point and confidence intervals for the difference in experienced AE proportion between treatment groups will be estimated with a generalized linear mixed model (GLMM), assuming a binomial distribution and identity link. GLMMs are a flexible generalization of the linear mixed effect model that allows response outcomes to have an error distribution other than the normal distribution (McCullagh, & Nelder, 1989). Statistical analysis modeling will be carried out utilizing SAS/STAT PROC GLIMMIX (SAS Institute Inc. 2017) with the general structure of the SAS code for this model is listed below:

```
proc glimmix data=anlyaedata;
  class patient treatment;
  model any_ae = treatment / link=identity dist=binomial;
  random int / subject=patient;
run;
```

A similar model will be run for the difference in proportion of withdrawn subjects due to adverse events between treatment groups. If the above specified models cannot be fit due to limitations of the study data, frequencies will be analyzed using chi-square test.

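### The SAP states three different windows for the between-arm adverse event comparison, and the 8 weeks in its only primary safety objective conflicts with 12 weeks of treatment and AE collection to Week 14

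*SAP*

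**What the plan says.** **Windows in the SAP.**
- Section 3.1.1 lists one primary safety objective: "Determine if adverse event rates, severity, and relatedness differ between the BUP/NLTRX group compared to the placebo group over the 8-week study period".
- Its parent section, 3.1, says the aim is to "compare safety and efficacy endpoints in the treatment group versus placebo after 8 weeks (with an additional follow up period extending to 12 weeks".
- Section 9.5.1, which holds the AE methods, sets no 8-week limit: "Summaries will include the number of individuals experiencing events over the duration of the study". It summarises by arm and by severity, and models any AE, any serious AE and any related AE.
- Section 9.2 defines the AE outcome as treatment-emergent events and gives no last day for that term.

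**The trial's own timeline.**
- Protocol 6.1.9: "The duration of therapy is 12 weeks". SAP 4.1 agrees: participants are randomized "to receive one of two treatments in a double-blind fashion for 12 weeks". SAP 9.2 places the injections at baseline, Week 4 and Week 8.
- Protocol 8.3: "AEs are collected from time of first dose taken after randomization through Week 14 follow-up visit".
- Protocol 2.3.1: "The investigators have designed the study to include two weeks (from Week 12 to Week 14) to monitor the patient for drug discontinuation or withdrawal".

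**Withdrawal scales.** The schedule in Protocol 7.3.1 has COWS and CIWA-Ar at Weeks 12 and 14. Protocol 10.4.4 plans between-group comparisons that include "3) side effect scales", without naming the scales.

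**The concern.** A primary safety objective should cover at least the period of exposure. This one ends at the visit where the third injection is given, so the dosing interval after that injection is outside it, as are the two weeks after study drug stops. Neither objective statement (3.1 or 3.1.1) reaches Week 14. The post-drug period is covered only by the undefined whole-study phrase in 9.5.1.

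Two things are at stake. First, an analyst following 3.1.1 and another following 9.5.1 could report different results as the answer to the same primary safety objective. If the window is not fixed before database lock, it could be chosen after unmasking. Second, Protocol 2.3.1 states that no taper is needed and that withdrawal symptoms are not expected. The Week 12 to 14 data bear most directly on that statement. They include COWS, for which the SAP plans no analysis.

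**Working it through.** **Inputs**
- Objective window: 8 weeks (SAP 3.1.1).
- Parent window: 12 weeks (SAP 3.1).
- AE methods window: whole study (SAP 9.5.1), read here as to Week 14.
- Treatment: 12 weeks (Protocol 6.1.9, SAP 4.1).
- Post-drug monitoring: 2 weeks (Protocol 2.3.1).
- Injections: baseline, Week 4, Week 8 (SAP 9.2).
- Participant duration: 14 weeks from randomization (Protocol Summary).

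**Step 1: reproduce the plan's own figure.** Treatment + post-drug monitoring = 12 + 2 = 14 weeks. This matches the stated participant duration and the end of AE collection in Protocol 8.3.

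**Step 2: what each window W leaves out.** AE-collection weeks omitted = (14 − W)/14. Treatment weeks omitted = (12 − W)/12, or zero if W is 12 or more.

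| Source | W | AE weeks omitted | Treatment weeks omitted | Post-drug weeks omitted |
|---|---|---|---|---|
| SAP 3.1.1 | 8 | 6/14 = 43% | 4/12 = 33% | 2 of 2 |
| SAP 3.1 | 12 | 2/14 = 14% | 0 | 2 of 2 |
| SAP 9.5.1 | 14 | 0 | 0 | 0 |

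**Step 3: exposure outside the 8-week reading.** Daily sublingual doses: 4 × 7 = 28 of 12 × 7 = 84, approximately, because the first tablet is taken the day after the first injection. Two of the three injections are given before Week 8. The third is given at Week 8, so the interval after it is outside.

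**Step 4: effect on the estimate.** The modelled quantity is whether a participant has at least one AE. For a given participant, lengthening the window can change the answer from no to yes but never from yes to no. Each arm's proportion can therefore only stay the same or rise as W goes from 8 to 12 to 14, and the risk difference can move in either direction. The documents give no AE rates by period, so the size of the shift cannot be calculated.

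**Step 5: trace COWS through the SAP.** COWS is in the assessment schedule. It is absent from the outcome definitions (9.2), the safety methods (9.5) and the list of planned tables and figures (Appendix B). Protocol 2.3.1 says opioid withdrawal signs and symptoms are assessed at the end of the study, so the data are intended to be informative.

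**The case against.** The best defence is that the operative text is 9.5.1, not 3.1.1. Section 9.5.1 counts events over the whole study, by arm, with no 8-week cut. SAP 3.2.3 sets no cut either, and refers to Protocol section 8, which collects AEs to Week 14. Protocol 10.4.4, the AE table in Appendix B and the data monitoring board listing in Appendix A are also unrestricted. The same 8-week phrase closes all three efficacy objectives in SAP 3.1.2, so it may be shared wording and not a deliberate safety cut-off, although the documents do not say.

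That defence stands against one tempting inference: that the last dosing period and the discontinuation period will be left out of the safety analysis. The documents do not support this. Under 9.5.1 late events would probably be counted. Discontinuation symptoms can also enter as AEs, because Protocol 7.3.5 assesses them at Week 14.

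The defence does not remove the conflict. The whole-study phrase is undefined, and SAP 9.1 describes analyses using data through Week 12, though mainly about efficacy. Apart from the protocol history, no SAP objective or analysis section names Week 14.

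Two further inferences should also be resisted:
- **CIWA-Ar is not a study-drug discontinuation measure.** Protocol 7.1.1 defines it as an alcohol withdrawal scale, and 7.3.2 repeats it at Weeks 12 and 14 to confirm medical stability for referral.
- **Protocol 10.4.4 is not a clear commitment to analyse COWS.** The scales are not named there, and 7.1.1 gives COWS an eligibility purpose. The case for analysing COWS rests on its Week 12 and 14 schedule and on Protocol 2.3.1.

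**Conclusion.** The point holds as an inconsistency between stated windows and as a mismatch between the primary safety objective and the trial's own timeline. Depending on which SAP section governs, the share of AE-collection weeks outside the comparison is 43%, 14% or 0%. These are shares of calendar time, not of events. They assume a participant followed to Week 14 and the whole-study phrase read as Week 14. The estimate of the probability of at least one AE depends on the choice, by an amount the documents do not allow one to compute.

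The absence of any planned COWS analysis stands however the window is settled. The point affects no sample size, power figure or efficacy test. It should be corrected before database lock, because the SAP as written leaves open which result answers its primary safety objective.

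**What to change.** 1. In SAP 3.1.1 and 3.1, set the safety comparison to run from first dose through Week 14, matching Protocol 8.3. State the same window in 9.5.1 in place of the undefined whole-study wording.
2. In SAP 9.2, define treatment-emergent and give it that same end date.
3. Keep an 8-week result if wanted, labelled as a sub-window and not as the answer to the primary safety objective.
4. Report by arm the AEs that start after the end of study drug. Splitting the whole timeline into further periods is a display choice and is not required.
5. Add COWS to 9.2, 9.5 and Appendix B as a by-arm summary at Weeks 12 and 14, presented as the opioid-withdrawal result. CIWA-Ar may be tabulated too, as an alcohol-withdrawal measure only.

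**Cost:** SAP wording plus one or two extra tables. All the data are already collected. No visits, sample size or clinical procedures change.

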3.1.2 Primary Efficacy Objectives

1. To evaluate the efficacy of BUP/NTRX in the treatment of comorbid PTSD and moderate-to-severe AUD based on a matrix outcome of response in terms of both PTSD and AUD outcomes over the 8-week study period.
2. Determine if percent of heavy drinking days (defined as >4 standard drinks/sessions for men and >3 standard drinks/sessions for women) as assessed by the Timeline Follow-Back (TLFB) are reduced for BUP/NTRX treatment over the 8-week study period.
3. Determine if PTSD symptoms, as measured by the change in the Clinician Administered PTSD Scale for DSM-5 (CAPS-5), are reduced for BUP/NTRX treatment over the 8-week study period.

3.1.3 Exploratory Efficacy Objectives

1. Examine if longer treatment is needed to show efficacy in the primary outcome measure between treatment groups at week 12.

3.2 Outcomes

A brief description of the safety and efficacy outcomes are described below. Additional detail regarding the definition of each of these outcomes is located in Section 9.2.

3.2.1 Primary Efficacy Outcomes

As mentioned above, the **primary outcome** is a matrix outcome of response in terms of both PTSD and AUD outcomes. The derivation of this measure will be a binary “yes/no” outcome. The PTSD outcome will be assessed using the CAPS-5 and be defined as “yes” if there is a decrease ≥ 10 points from baseline to week 8. The AUD outcome will be assessed using the TLFB and %HDD. The AUD outcome will be defined as “yes” if there is a reduction >1 -shift in World Health Organization (WHO) risk levels of alcohol use from baseline to week 8 (note: the look-back period will consist of 28 consecutive days).

As a complement to the primary outcome, we will also examine each of the components individually (CAPS-5 Total Symptom Severity Score and %HDD)

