4.2 ENDPOINTS

4.2.1 PRIMARY ENDPOINT

Primary Hypothesis: Compared to the PLC group, a proportionally higher number of participants will respond to treatment with SL-BUP + XR-NTX, as defined as decrease ≥ 8 points on the Clinician Administered PTSD Scale for DSM-5 (CAPS-5) and reduction ≥ 1 -shift in World Health Organization (WHO) risk levels of alcohol use disorder, as assessed on the Timeline Follow-Back (TLFB)¹⁸ from baseline to Week 8. **The primary efficacy endpoint** is a reduction of both AUD and PTSD symptoms, such that lowering both will be coded success and any other outcome will be failure. All group comparisons will be made.

As a complement to the primary hypothesis, we will also examine each of the components individually. Compared to PLC group, SL-BUP + XR-NTX will significantly reduce PTSD symptoms, as measured by the change in CAPS-5 over an 8-week treatment period. Compared to PLC group, SL-BUP + XR-NTX will be more effective in decreasing heavy alcohol use at 8 weeks. This outcome is the percent of heavy drinking days (defined as *>4 standard drinks/sessions for men and >3 standard drinks/sessions for women*) as assessed by the TLFB.

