10.4.2 ANALYSIS OF THE PRIMARY EFFICACY ENDPOINT(S)

The primary dependent variable will be response status at Week 8 for each participant. A positive response is defined as a decrease from baseline of at least 8 points on the CAPS-5 score and a reduction of at least 1 risk level of alcohol use, as defined by WHO, at Week 8. Response data will be analyzed using mixed logistic regression with treatment group, measurement visit as a categorical variable, gender, site, presence/absence of anti-depressants, and other potential confounders as explanatory variables. A treatment group by measurement visit interaction will be included to account for the longitudinal nature of the data with the Week 8 effect being the primary outcome of interest. A two-sided p-value will be reported from the primary analysis for the all pairwise comparisons of SL-BUP/XR-NTX treatment and placebo groups.

As a complement to the primary outcome, the AUD and PTSD components of the composite will be evaluated individually. Difference in heavy alcohol use at Week 8 (defined as *>4 standard drinks/sessions for men and >3 standard drinks/sessions for women*) will be analyzed using a generalized-linear mixed model with treatment group, gender, site, presence/absence of anti-depressants, and other potential confounders as explanatory variables. Difference in reduction of PTSD symptoms at Week 8 (as measured by the CAPS-5) will be analyzed using a generalized-linear mixed model with treatment group, gender, site, presence/absence of anti-depressants, and other potential confounders as explanatory variables. For both outcomes, a treatment group by visit interaction term will be included to account for the longitudinal nature of the data, with Week 8 effect being the primary outcome of interest.

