STATISTICAL ANALYSIS PLAN

Protocol Number: AS140026-A5

Kappa Opioid Receptor Antagonism for the Treatment of Alcohol Use Disorder and Comorbid PTSD

SAP VERSION: V4.0

SAP DATE: August 2019

PI/SPONSOR:
[name]
[name]

PREPARED BY:
RTI International.
[name]
[name]

AUTHOR (S):
[name]
[name]

Network

AS140026-A5 Statistical Analysis Plan

Version #	Implemented By	Revision Date	Approval Date	Reason
1.0	[name]	N/A	N/A	First version in Draft Protocol Amendment Version 7 is pending approval
2.0	[name]	02/23/2022	N/A	
1. Changed the Fear Potentiated Startle (FPS) outcome data from secondary to exploratory outcome2. Added further clarification for the TLFB derived outcome measures
3.0	[name]	03/29/2022	N/A	Removed evaluation of the FPS assessment from this primary SAP; those analyses will be detailed in a secondary supplemental SAP, as needed
4.0	[name] and [name]	04/19/2022	N/A	
1. For the primary outcome definition, changed a positive response for PTSD from a ≥ 8 point CAPS-5 decrease from baseline to ≥ 10 point decrease from baseline;2. Clarified that the AUD outcome measure is the average number of drinks consumed over a 28 consecutive day look-back period (and not based on drinking days)3. Added change in PeTH value from baseline to Weeks 8 and 12 to exploratory outcomes

The undersigned acknowledge they have reviewed the **Statistical Analysis Plan** and agree with the approach it presents. Changes to this **Statistical Analysis Plan** will be coordinated with and approved by the undersigned or their designated representatives.

Signature: _____ Date: _____

Print Name: [name]

Title: Study Clinical Lead

Role: Principal Investigator

Signature: _____ Date: _____

Print Name: [name]

Title: Senior Statistician

Role: Senior Statistician/Alternate-PI

Signature: _____ Date: _____

Print Name: [name]

Title: Statistician

Role: Lead Statistician

Contents

1 BACKGROUND AND PROTOCOL HISTORY	4
2 PURPOSE OF THE ANALYSES	6
3 STUDY OBJECTIVES AND OUTCOMES	7
3.1 STUDY OBJECTIVES	7
3.1.1 PRIMARY SAFETY OBJECTIVES	7
3.1.2 PRIMARY EFFICACY OBJECTIVES	7
3.1.3 EXPLORATORY EFFICACY OBJECTIVES	7
3.2 OUTCOMES	7
3.2.1 PRIMARY EFFICACY OUTCOMES	8
3.2.2 EXPLORATORY EFFICACY OUTCOMES	8
3.2.3 SAFETY OUTCOMES	8
4 STUDY METHODS	8
4.1 OVERALL STUDY DESIGN AND PLAN	8
4.2 STUDY POPULATION	9

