9.2 Efficacy and Safety Outcome Variables

Variable	Type	Definition														
Primary Outcomes																
Composite AUD + PTSD outcome	Binary (Yes/No)	
A positive response is defined as a decrease from baseline of at least 10 points on the CAPS-5 score (Schnurr et al., 2022) and a reduction of at least 1 risk level of alcohol use, as defined by WHO, at week 8. AUD data is collected on the TLFB, a semi-structured interview that uses a calendar prompt and other memory aids to facilitate accurate recall of the numbers of drinks consumed each day during a given target period (Sobell et al., 1996). The definition of WHO risk drinking levels are defined by Knox et al. (2018), and displayed in the below table
 
  
 Wave 1 WHO risk drinking level	Definition of each level, in grams (US standard drinks)	
   
 Very high	>100 g (>7.1 drinks) for men;	
 
 >60 g (>4.3 drinks) for women	
 
 High	60–100 g (4.3–7.1 drinks) for men;	
 
 40–60 g (2.9–4.3 drinks) for women	
 
 Moderate	40–60 g (2.9–4.3 drinks) for men;	
 
 20–40 g (1.4–2.9 drinks) for women	
 
 Low	1–40 g (<2.9 drinks) for men;	
 
 1–20 g (<1.4 drinks) for women	
  
	Wave 1 WHO risk drinking level	Definition of each level, in grams (US standard drinks)	Very high	>100 g (>7.1 drinks) for men;	>60 g (>4.3 drinks) for women	High	60–100 g (4.3–7.1 drinks) for men;	40–60 g (2.9–4.3 drinks) for women	Moderate	40–60 g (2.9–4.3 drinks) for men;	20–40 g (1.4–2.9 drinks) for women	Low	1–40 g (<2.9 drinks) for men;	1–20 g (<1.4 drinks) for women
Wave 1 WHO risk drinking level	Definition of each level, in grams (US standard drinks)															
Very high	>100 g (>7.1 drinks) for men;															
	>60 g (>4.3 drinks) for women															
High	60–100 g (4.3–7.1 drinks) for men;															
	40–60 g (2.9–4.3 drinks) for women															
Moderate	40–60 g (2.9–4.3 drinks) for men;															
	20–40 g (1.4–2.9 drinks) for women															
Low	1–40 g (<2.9 drinks) for men;															
	1–20 g (<1.4 drinks) for women															

Variable	Type	Definition

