		
The TLFB assessment is given at screening, baseline, and weeks 1, 2, 4, 6, 8, 10, and 12. The screening measurement uses a 90-day recall period whereas the subsequent (post treatment follow up) measurements use a recall period of “since the last measurement.” The baseline WHO risk level will be derived from TLFB data collected at both the screening and baseline visit. The look-back period to define the WHO risk level will be conducted over 28 consecutive days and based on the average number of reported standard drinks during those 28 consecutive days. Each derived outcome measure for a specific timepoint will be based on the baseline visit date. In the event 28 consecutive days are not captured for the full look-back period, participant data will be excluded from analyses in the event the number of total days included in look-back period is less than one standard deviation of the entire population.

Percent Heavy Drinking Days (%HDD)	Continuous (range between 0 and 100)	
Percent Heavy Drinking Days (%HDD) is measured via the Timeline Follow Back instrument (Sobell et al., 1996). The screening (baseline) measurement uses a 90-day recall period whereas the subsequent (post treatment follow up) measurements use a recall period of “since the last measurement.” Baseline %HDD will be derived from TLFB data collected at both the screening and baseline visit. The look-back period to define %HDD will be conducted over 28 consecutive days and based on the number of heavy drinking days reported during this time period. Each derived outcome measure for a specific timepoint will be based on the baseline visit date. In the event 28 consecutive days are not captured for the full look-back period, participant data will be excluded from analyses in the event the number of total days included in look-back period is less than one standard deviation of the entire population.
 
A heavy drinking day is defined as follows:
 
>4 standard drinks/sessions for men and >3 standard drinks/sessions for women

Variable	Type	Definition
CAPS-5 Total Symptom Severity Score	Continuous (range between 0 and 80)	CAPS-5 total symptom severity score is measured via the Clinician-Administered PTSD Scale For DSM-5 (CAPS-5). The score is calculated by summing severity scores for the 20 DSM-5 PTSD symptoms (Weathers et al., 2013), with a higher score indicating worse PTSD symptoms.
Exploratory Outcomes		

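### SAP 3.2.1 asks for a drop of more than one WHO drinking level where four other places ask for at least one, and the level table leaves a Low baseline nothing to drop to

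*SAP*

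**What the plan says.** The primary endpoint is a yes/no composite that needs both a PTSD response and an AUD response. This point concerns the AUD half only.

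- SAP 3.2.1 scores it as met "if there is a reduction >1 -shift in World Health Organization (WHO) risk levels of alcohol use from baseline to week 8".
- Protocol 4.2.1 has nearly the same phrase with a different symbol: "reduction ≥ 1 -shift in World Health Organization (WHO) risk levels of alcohol use disorder".
- Protocol 10.4.2 asks for "a reduction of at least 1 risk level of alcohol use, as defined by WHO, at Week 8".
- SAP 9.2 asks for "a reduction of at least 1 risk level of alcohol use, as defined by WHO, at week 8", and SAP 9.3 repeats the at-least-one rule.

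SAP 3.2 calls its own account brief and sends the reader to 9.2 for the detail. In the SAP version history, the v4.0 entry on this measure begins "Clarified that the AUD outcome measure is the average number of drinks consumed over a 28 consecutive day look-back period". The v2.0 entry speaks only in general terms of clarifying the TLFB measures. No entry mentions a change in the number of levels.

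The table in SAP 9.2 has four levels: Very high, High, Moderate and Low. Low is "1–40 g (<2.9 drinks) for men" and "1–20 g (<1.4 drinks) for women". The level is "based on the average number of reported standard drinks during those 28 consecutive days".

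Protocol 5.1, criterion 3, requires 21 drinks a week (men) or 14 (women) in at least two weeks of a four-week interval within the 90 days before baseline. It glosses this as Moderate risk or above. SAP 9.3 mentions, as a possibility, a sensitivity analysis without participants who are Low or Moderate at baseline.

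**The concern.** There are two separate defects in one definition.

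First, the section of the SAP that is titled as the primary outcome gives a different threshold from the rest of the plan. On a four-level scale, the step from at least one to more than one decides which participants can respond at all.

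Second, whichever symbol is used, the table stops at Low and does not settle what 0 drinks is. The drinks column for Low has only an upper limit, so it includes 0. The grams column starts at 1 g, so it does not. In a trial that treats alcohol use disorder, abstinence is a result that the scoring rule should name.

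This variable carries the single formal hypothesis test (SAP 7.7). Its coding should not depend on which section a programmer reads, nor be settled after unmasking.

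**Working it through.** **The plan's own figure.** The only stated number that depends on the responder definition is the power for 5/45 against 17/45 in Protocol 10.5, given as 0.795. With the Walters approximation:

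Φ(√(4·45·45/90) · [asin√(17/45 − 1/90) − asin√(5/45 + 1/90)] − 1.96) = 0.7946

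The figure reproduces and is not in dispute.

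**Step 1: which changes count under each rule.** Number the levels Low 1, Moderate 2, High 3, Very high 4, and list every Week 8 level that counts as a response.

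| Baseline | Drop of at least 1 | Drop of more than 1 | At least 1, with Abstinent = 0 added |
|---|---|---|---|
| Low | none | none | Abstinent |
| Moderate | Low | none | Low, Abstinent |
| High | Moderate, Low | Low | Moderate, Low, Abstinent |
| Very high | High, Moderate, Low | Moderate, Low | High, Moderate, Low, Abstinent |

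Response is possible from 3 of 4 baseline levels under at least 1, from 2 of 4 under more than 1, and from 4 of 4 if an Abstinent level is added.

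**Step 2: can an eligible participant be Low at baseline?** The inputs are the weekly minimum in Protocol 5.1 and the 28-day average and Low ceilings in SAP 9.2 (2.9 drinks a day for men, 1.4 for women). The formula is average = (weekly minimum × qualifying weeks)/28. It assumes that the 28 days end at baseline, contain the qualifying weeks, and have no drinking in the other weeks.

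| Weeks at the minimum | Men (21 a week) | Women (14 a week) |
|---|---|---|
| 2 | 42/28 = 1.5, Low | 28/28 = 1.0, Low |
| 3 | 63/28 = 2.25, Low | 42/28 = 1.5, Moderate |
| 4 | 84/28 = 3.0, Moderate | 56/28 = 2.0, Moderate |

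Two weeks are enough for entry, so a Low baseline is reachable for both sexes despite the gloss in criterion 3. With no other drinking, the two weeks would need 2.9 × 28/2 = 40.6 drinks each (men) or 1.4 × 28/2 = 19.6 (women) to bring the 28-day average to Moderate.

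These two-week examples do not depend on the column. The table implies about 14 g per drink (60/4.3 = 14.0; 100/7.1 = 14.1). At 14 g, 1.5 drinks is 21 g and 1.0 drink is 14 g, and both are Low by grams as well.

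**Step 3: what 0 drinks scores.** By the drinks column, 0 is Low. By the grams column, 0 has no level. From a Low baseline, the first reading gives no change and the second gives nothing to compare. Neither yields a reduction. From Moderate or above, the drinks column makes an abstainer a responder under the at-least-one rule, so the gap bears mainly on Low baselines.

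**The case against.** The strongest reply is that the first part is editorial. SAP 3.2 defers to 9.2; 9.2 and the analysis section 9.3 both say at least one; no change is logged. The symbol may be a lost underline: the SAP also prints strict inequalities for the CIWA-Ar and QTcF criteria where the protocol has non-strict ones. All of this stands, and it makes misuse unlikely. It does not remove the contradiction, and the greater-or-equal sign for the PTSD half survives in the same paragraph of 3.2.1. Only the source file can settle that. If it shows the non-strict sign, the first part falls away and the second is untouched.

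On the second part, a four-level rule fixed in advance scores a Low-baseline participant as a non-responder by definition, and adding a level changes the endpoint. That is fair. The defect is that abstinence is not defined, not that anyone is coded wrongly.

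Some stronger readings are tempting, but the documents do not support them:

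- A reader might infer that the optional analysis in SAP 9.3 shows a two-level rule was intended, because the levels it leaves out are those that cannot respond under more than one. SAP 9.3 itself states at least one level.
- A reader might infer that a Low-baseline participant who stops drinking is expressly scored as Low. That follows from the drinks column only; by grams, 0 has no level.
- A reader might set up one-drink contrasts at the Low ceiling. These depend on the column: 81 drinks in 28 days is 2.89 a day (Low), but at 14 g per drink it is 40.5 g (Moderate).

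**Conclusion.** Both parts hold, and both are worth fixing. The threshold in SAP 3.2.1 contradicts four other statements of the same rule, and at least one level is evidently intended. Programmed literally, it would shut out Low and Moderate baselines and require a two-level drop from High and Very high. With the symbol corrected, the Low baseline still has no scorable reduction, even at abstinence, and eligible participants can start there. SAP 9.3 itself allows for Low baselines.

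The size in participants is unknown, because the documents give no baseline distribution of WHO levels. A reader might infer a loss of power or a bias between arms, and neither is supported. Any power figure would need an assumed share of Low baselines. It would also need the further assumption that the planned 11% and 38% response rates leave those participants out. The same rule applies to both randomized arms. The baseline examples rest on the 28-day window ending at baseline and containing the qualifying weeks, with no other drinking in it.

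**What to change.** Make these changes before unmasking and log them in the SAP.

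1. In SAP 3.2.1, replace the more-than-one shift by at least one level, after checking the source file for a lost underline.
2. In SAP 9.2, state which column of the table governs and how 0 drinks is classed. Preferably add an Abstinent level (0 drinks) below Low, so that Low to Abstinent counts as one level, and report the four-level version as a sensitivity analysis.
3. If the four-level primary is kept, turn the optional analysis in SAP 9.3 into a definite one that leaves out Low baselines.

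The cost is one symbol, one table row, a sentence or two, a log entry and one sensitivity run, with no new patients or data. The small downside is that an Abstinent level is a logged amendment to the primary endpoint definition.
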